3.5.2 Population PK and exposure-response/safety analysis

A population PK model will be developed using a non-linear mixed-effects modelling approach in patients with NSCLC where possible. The impact of physiologically-relevant patient characteristics (covariates) and disease on PK will be evaluated. The relationship between PK exposure and the effect on safety and efficacy will be evaluated, if appropriate. The results of such an analysis will be reported in a separate report.

3.5.3 Immunogenicity analysis

Immunogenicity results will be analysed descriptively by summarizing the number and percentage of patients who develop detectable anti-MEDI4736 antibodies. The immunogenicity titre will be reported for samples confirmed positive for the presence of anti-MEDI4736 antibodies. Summaries will be based upon all patients from the safety population. The effect of immunogenicity on PK, PDx, efficacy and safety will be evaluated, but such analyses, if applicable, will be reported in a separate report.

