c Creatinine clearance, magnesium, amylase, lipase, and uric acid tested at Screening and every 4 weeks thereafter. Urinalysis performed at Screening, Day 1, every 4 weeks and as clinically indicated.

- d Coagulation tests at Screening: prothrombin time, APTT and INR – only performed at Screening and as clinically indicated.
- e **For ADA, sPD-L1:** These assessments will be performed pre-infusion on Day 1, Week 8, Week 24 and Week 48. **PK samples** should be collected on Day 1, Week 8, Week 24 and Week 48. Only on Day 1 (randomisation visit) and at Week 24 before and after the infusion. At Week 8 and Week 48, only a pre-dose sample will be collected. Pre-dose samples can be taken within 60 minutes before infusion and the end-of-infusion samples within 10 minutes after the end of infusion. **Circulating soluble factors** assessment will be performed pre-infusion on Day 1, Week 4 and Week 12. **For miRNA/mRNA** the assessment will be performed pre-infusion on Day 1, Week 8 and Week 48.

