### **12.1.2 Safety analysis set**

All patients who received at least one dose of randomised study drug (MEDI4736 or placebo) and for whom any post-dose data are available will be included in the safety population. Throughout the safety results sections, erroneously treated patients (eg, those randomised to Treatment A but actually given Treatment B) will be accounted for in the actual treatment arm.

When assessing safety and tolerability, summaries will be produced based on the safety analysis set.

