2. ANALYSIS SETS

2.1 Definition of Analysis Sets

Four main analysis sets are defined for this study.

Full analysis set (FAS) (Intention to treat (ITT)):

The primary statistical analysis of the efficacy of MEDI4736 vs placebo will include all randomised patients and will compare the treatment arms on the basis of randomised treatment, regardless of the treatment actually received. Patients who were randomised but did not subsequently go on to receive study drug are included in the ITT population. Note, this is also known as the FAS. Therefore, all efficacy and HRQoL data will be analysed using the FAS on an ITT basis.

Safety analysis set:

All patients who received at least one dose of randomised study medication, MEDI4736 or placebo, (regardless of whether that was the randomised therapy intended or indeed whether, in rare cases, they received therapy without being randomised) will be included in the safety population. Throughout the safety sections, erroneously treated patients (e.g., those randomised to Treatment A but actually given Treatment B) will be accounted for by the actual treatment administered. As long as a patient received any dose of MEDI4736, the patient would be counted under MEDI4736 treatment group.

When assessing safety and tolerability, summaries will be produced based on the safety analysis set.

PK analysis set:

All patients who receive at least 1 dose of MEDI4736 per the protocol, for whom any post-dose data are available and do not violate or deviate from the protocol in ways that would significantly affect the PK analyses will be included in the PK analysis set. The population will be defined by the Study Team Physician, Pharmacokineticist and Statistician prior to any analyses being performed.

Table 1 gives a summary of outcome variables and analysis populations.

Table 1 Summary of outcome variables and analysis populations

Outcome variable	Populations
Efficacy Data	
OS (co-primary)	FAS (ITT)
PFS (co-primary)	FAS (ITT)
OS24, APF12, APF18, PFS2, DoR, TTDM, TFST, PRO endpoints, World Health Organisation performance status	FAS (ITT)
ORR	FAS (ITT)
Study Population/Demography Data	
Demography characteristics (e.g. age, sex etc.)	FAS (ITT)
Baseline, disease characteristics	FAS (ITT)
Analysis populations	FAS (ITT)
Important deviations	FAS (ITT)
Medical/Surgical history	FAS (ITT)
Previous anti-cancer therapy	FAS (ITT)
Concomitant medications/procedures	FAS (ITT)
Subsequent anti-cancer therapy	FAS (ITT)

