3.4.2 Laboratory data

Laboratory data will be collected throughout the study, from screening to follow-up visit as described in the CSP. Blood and urine samples for determination of haematology, clinical chemistry, and urinalysis will be collected as described in Section 6.4.5 of the CSP. For the definition of baseline and the derivation of post baseline visit values considering visit window and how to handle multiple records, derivation rules as described in [Section 4.1.3](#) below will be used.

Change from baseline in haematology and clinical chemistry variables will be calculated for each post-dose visit on treatment. CTCAE grades will be defined at each visit according to the CTCAE grade criteria using local or project ranges as required, after conversion of lab result to corresponding preferred units. The following parameters have CTCAE grades defined for both high and low values: Potassium, Sodium, Magnesium, Glucose and Corrected calcium so high and low CTCAE grades will be calculated.

Corrected calcium will be derived during creation of the reporting database using the following formula:

$$\text{Corrected calcium (mmol/L)} = \text{Total Calcium (mmol/L)} + ([40 - \text{Albumin (G/L)}] \times 0.02)$$

Creatinine clearance will be derived according to the Cockcroft-Gault formula ([Cockcroft and Gault 1976](#)).

Males:

$$\text{Creatinine CL} = \frac{\text{Weight (kg)} \times (140 - \text{Age})}{72 \times \text{serum creatinine (mg/dL)}}$$

Females:

$$\text{Creatinine CL} = \frac{\text{Weight (kg)} \times (140 - \text{Age})}{72 \times \text{serum creatinine (mg/dL)}} \times 0.85$$

Absolute values will be compared to the project reference range and classified as low (below range), normal (within range or on limits of range) and high (above range).

The maximum or minimum on-treatment value (depending on the direction of an adverse effect) will be defined for each laboratory parameter as the maximum (or minimum) post-baseline value at any time.

Local reference ranges will be used for the primary interpretation of laboratory data at the local laboratory. Project reference ranges will be used throughout for reporting purposes. The denominator used in laboratory summaries of CTCAE grades will only include evaluable patients, in other words those who had sufficient data to have the possibility of an abnormality.

For example:

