4.1 General Principles

Efficacy and HRQoL data will be summarised and analysed on the ITT analysis set. Safety and treatment exposure data will be summarised based upon the safety analysis set. Study population and demography data will be summarised based upon the ITT analysis set.

Efficacy from the re-treatment period may be summarised separately for the site investigator data. For the site investigator data, any derivations relative to baseline (e.g. day, RECIST derivations) in the re-treatment period will be relative to the baseline scan prior to the re-treatment. To avoid biasing the blinded central reviewers (i.e., when determining progression) the baseline scans prior to re-treatment will not be identified (see further the BICR charter) thus no efficacy data will be summarised from the re-treatment period based upon BICR.

Safety data will be summarised from the initial treatment period. Safety data from the re-treatment period may also be summarised via a small set of headline summaries should there be sufficient number of patients re-treated to warrant this. Any safety summaries representing the re-treatment period will be based upon a subset of the safety analysis set representing patients who have had at least one dose of study treatment in the re-treatment period.

The below mentioned general principles will be followed throughout the study:

- Descriptive statistics will be used for all variables, as appropriate. Continuous variables will be summarised by the number of observations, mean, standard deviation, median,

minimum, and maximum. For log transformed data it is more appropriate to present geometric mean, coefficient of variation (CV), median, minimum and maximum. Categorical variables will be summarised by frequency counts and percentages for each category.

- Unless otherwise stated, percentages will be calculated out of the population total and for each treatment group.
- For continuous data the mean and median will be rounded to 1 additional decimal place compared to the original data. The standard deviation will be rounded to 2 additional decimal places compared to the original data. Minimum and maximum will be displayed with the same accuracy as the original data.
- For categorical data, percentages will be rounded to 1 decimal place.
- SAS® version 9.2 will be used for all analyses.

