4.2.7 Immunogenicity analysis

Immunogenicity results will be listed and a summary will be provided of the number and percentage of patients who develop detectable anti-MEDI4736 antibodies based on the safety population. The immunogenicity titre and neutralising ADA data will be listed for samples confirmed positive for the presence of anti-MEDI4736 antibodies. The effect of immunogenicity on PK, PDx, efficacy and safety will be evaluated if data allow. These outputs will be produced by AstraZeneca/MedImmune Clinical Pharmacology group or designee.

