6. CHANGES OF ANALYSIS FROM PROTOCOL

Table 9 Changes from the planned analysis

Section of SAP Affected (If applicable)	Change	Rationale
4.2.3 Patient Reported Outcomes	Add sensitivity analysis for primary PRO endpoints where RECIST progression counts as an event	To explore the effect of RECIST progression on the PRO endpoint analyses
2.1 Definition of Analysis Sets	Remove criteria that patients need to have post-dose data to be included in the safety analysis set	More widely used definition and to be consistent with other studies
Section 3.2.2.7 Time to death of Distant Metastasis	Clarified definition of Time to death or distant metastasis	Added further detail based on data will be collected
Section 4.2.1.1 Overall Survival	Removed global interaction test for subgroup analyses, subgroups will be tested using model only including treatment	More widely used definition and to be consistent with other studies
Section 4.2.2.1	Remove HR and added p-value to the presentation of OS12	p-value required for multiple testing procedure
Section 4.2.2.4/5	Change presentation of proportion of patients alive and progression free at 12 and 18 months	To match TFL standards
Section 4.2.2.3 Duration of Response	Removed analysis of Duration of Response	Not required
Section 4.2.3.3	Added mixed models repeated measures for analyses of PRO endpoints	To explore the treatment effect using change from baseline data

Section 3.2.1.2, 3.2.2.2, 3.2.2.7	Clarify criteria for censoring in the setting of no progression or death from last evaluable RECIST 1.1 assessment to last RECIST 1.1 assessment	*See below
-----------------------------------	--	------------

*Rationale for the change:

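### The anti-drug antibody (ADA) percentage is taken over every dosed patient, including those with no post-dose ADA result, and the numerator is not tied to the Day 1 sample

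*SAP*

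**What the plan says.** SAP 3.5.3 summarises the number and percentage of patients with detectable antibodies and states: "Summaries will be based upon all patients from the safety population". SAP 4.2.7 repeats it, asking for the "percentage of patients who develop detectable anti-MEDI4736 antibodies based on the safety population". SAP Table 1 also assigns immunogenicity data to the Safety set.

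SAP 4.1 supplies the default denominator: "Unless otherwise stated, percentages will be calculated out of the population total and for each treatment group". Nothing in the ADA sections states otherwise. Neither document defines an ADA-evaluable set, a rule for patients with no post-dose sample, or a requirement for a baseline result.

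SAP 2.1 defines the safety set as "All patients who received at least one dose of randomised study medication, MEDI4736 or placebo". SAP Table 9 records the departure from the protocol: "Remove criteria that patients need to have post-dose data to be included in the safety analysis set".

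Protocol Table 1, footnote e, schedules ADA and soluble PD-L1 sampling on treatment: "These assessments will be performed pre-infusion on Day 1, Week 8, Week 24 and Week 48". Protocol Tables 2 and 3 add ADA samples after the last dose.

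**The concern.** ADA incidence can be observed only in a patient who gives a sample after dosing. The first scheduled on-treatment sample after Day 1 is at Week 8. A patient who dies, withdraws or is lost before then, and gives no follow-up sample, cannot be found positive, yet still counts in the denominator.

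The SAP handles the same problem properly elsewhere. For laboratory toxicity, SAP 3.4.2 says "The denominator used in laboratory summaries of CTCAE grades will only include evaluable patients", and it asks for a baseline value where the grade depends on change. SAP 3.4.3 and 3.4.4 restrict ECG and vital-sign denominators to patients with recorded data. ADA has no equivalent rule.

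The numerator has a separate gap. The plan speaks of patients who *develop* antibodies but does not define this against the Day 1 pre-dose sample, although that sample is scheduled. Two programmers could treat a baseline-positive patient differently and obtain different rates from the same data.

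Immunogenicity is a named secondary objective (SAP 1.1.2). Protocol 1.4.2 lists ADA among the important potential risks, and Protocol 3.2.3.2 sets the target trough partly to allow for an ADA effect on exposure. The incidence figure should mean one defined thing.

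**Working it through.** The documents give no expected ADA incidence, no count of ADA-evaluable patients and no missing-sample rate for this trial. There is no stated figure to reproduce; what follows is illustration under stated assumptions.

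**Inputs**
- Planned MEDI4736 arm: 702 randomised 2:1 (SAP 1.3), so 702 × 2/3 = 468. The safety set could differ slightly.
- e: ADA rate among patients with a post-dose result. Assumed 5% and 10%. A third value, 3/19 = 15.8%, is the patient-level count from the first-in-human study in Protocol 3.2.3.2, used only as an example.
- m: share of the arm's safety set with no post-dose ADA result. Not given; assumed 2% to 20%.

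**Denominator effect**

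Reported rate = positives / N = e × (1 − m) × N / N = e × (1 − m). The relative shortfall equals m.

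| m (assumed) | Untested of 468 | e = 5% | e = 10% | e = 15.8% |
|---|---|---|---|---|
| 0 | 0 | 5.00% | 10.0% | 15.8% |
| 2% | about 9 | 4.90% | 9.8% | 15.5% |
| 5% | about 23 | 4.75% | 9.5% | 15.0% |
| 10% | about 47 | 4.50% | 9.0% | 14.2% |
| 20% | about 94 | 4.00% | 8.0% | 12.6% |

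In whole patients at m = 10%: 421 are evaluable. Twenty-one positives are 21/421 = 5.0% of those tested but 21/468 = 4.5% of the safety set.

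**Numerator effect**

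Let b be the share of the safety set that is positive at Day 1 and is counted as having developed ADA although nothing emerged on treatment. Then reported rate = e × (1 − m) + b, with e now the treatment-emergent rate. The net error is b − e × m. At e = 5%:
- m = 5%: the two effects cancel at b = 0.05 × 0.05 = 0.25%, about 1 patient in 468.
- m = 20%: they cancel at b = 0.05 × 0.20 = 1.0%, about 5 patients in 468.

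A handful of baseline-positive patients is therefore enough to reverse the sign. Neither b nor m is in the documents.

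**The case against.** The strongest reply is that the untested share should be small. Protocol 5.8.1 keeps patients who stop study drug in follow-up, including protocol-specified blood samples, and requires those who stop for an adverse event to attend all scheduled visits. Tables 2 and 3 schedule ADA samples after the last dose. This stands, and it limits m mainly to early deaths, consent withdrawals and patients followed only by phone. It does not bring m to zero by rule.

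Results are also to be listed (SAP 4.2.7; by patient in Protocol 12.2.13.1), so a rate among tested patients could be rebuilt. That helps a later reader but does not correct the percentage that the plan tells the programmer to report.

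Some stronger readings are tempting but not supported:
- A reader might infer that untested patients are classified as antibody-negative. The SAP never says so; they act as non-positives only because they are in the denominator.
- A reader might blame the dropped post-dose condition. The protocol's safety set asked for patients "for whom any post-dose data are available will be included in the safety population", meaning any data, not an ADA result. Restoring it would not cure the fault.
- A reader might infer that placebo patients dilute the MEDI4736 rate, or that the arms are distorted differently. Percentages are per treatment group, and the documents give no untested share by arm.

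**Conclusion.** The denominator rule is explicit and does not suit this variable: patients in whom ADA could not be observed are counted as at risk. The size is proportional to m, which is unknown and may be small. For a 5% rate among tested patients, the shortfall is 0.25 points at m = 5% and 1.0 point at m = 20%; at m = 0 there is none.

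A reader might go on to conclude that the reported incidence is understated overall. The documents do not support that. The undefined numerator can push the rate up by a similar or larger amount, so the net direction is not established. Nor does e × (1 − m) compare the reported figure with a true rate in all treated patients. It compares it with the rate in tested patients, and the two agree only if untested patients, who will often have had short exposure, would have had the same incidence.

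The analysis is descriptive with no between-arm test. Alpha, power and the co-primary endpoints are not touched.

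**What to change.** In SAP 3.5.3 and 4.2.7, with a matching note in SAP Table 1:
- Use as denominator the safety-set patients with at least one post-dose ADA result.
- Count treatment-emergent ADA relative to the Day 1 pre-dose result, among patients with both a baseline and a post-dose result.
- Report baseline-positive prevalence separately.
- State by arm how many safety-set patients were not evaluable.
- If a titre rise in baseline-positive patients is to count as treatment-emergent, the sponsor should pre-specify the criterion; the documents give no figure from which to set it.

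The cost is SAP wording and a few extra table rows. The samples are already scheduled, so no new data collection is needed.

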3.6 Exploratory Variables

The following exploratory variables will be included in the CSR.

3.6.1 EQ-5D-5L

As one of the exploratory objectives, the EQ-5D-5L health state utility index will be used to explore the impact of treatment and disease state on health state utility.

The EQ-5D is a standardised measure of health status developed by the EuroQol Group in order to provide a simple, generic measure of health for clinical and economic appraisal. Applicable to a wide range of health conditions and treatments, it provides a simple descriptive profile and a single index value for health status that can be used in the clinical and economic evaluation of health care.

The EQ-5D-5L index comprises 5 dimensions of health (mobility, self-care, usual activities, pain/discomfort and anxiety/depression). For each dimension, respondents select which statement best describes their health on that day from a possible 5 options of increasing levels of severity (no problems, slight problems, moderate problems, severe problems and unable to/extreme problems). A unique EQ-5D health state is referred to by a 5 digit code allowing for a total of 3125 health states. For example, state 11111 indicates no problems on any of the 5 dimensions. These data will be converted into a weighted health state index by applying scores from EQ-5D value sets elicited from general population samples (the base case will be the United Kingdom valuation set, with other country value sets applied in scenario analyses). Where values sets are not available, the EQ-5D-5L to EQ-5D-3L crosswalk (Oemar and Janseen 2013) will be applied. In addition to the descriptive system, respondents also assess their health on the day of assessment on a visual analogue scale, ranging from 0 (worst imaginable health) to 100 (best imaginable health). This score is reported separately.

The evaluable population will comprise a subset of the ITT analysis set who have a baseline EQ-5D-5L assessment.

Compliance rate of EQ-5D-5L will be analysed similarly using the method stated in Section 3.3.3.

3.6.2 Health Resource Use

Health resource use outcome variables include the following:

- Length of hospital stay
- Reasons for hospitalisation
- Length of any time spent in an intensive care unit (ICU)

The length of hospital stay will be calculated as the difference between the date of hospital discharge (or death date) and the start date of hospitalisation or start of study drug if the start

of study drug is after start date of hospitalisation (length of hospital stay = end date of hospitalisation – start date of hospitalisation or start date of study drug whichever is later + 1). For patients with missing discharge date, the last day with available data will be used as the end date of hospitalisation.

For patients who were hospitalised more than one time during the study period, the length of hospital stay will be the sum of all durations of hospital stays.

The length of ICU stay will be calculated using the same method as detailed above for the length of hospital stay.

